## 6.5 PROHIBITED MEDICATIONS

Treatment with any of the medications below will not be permitted, whether taken alone or as a component of a combination drug within previous 3 months. These medications can influence glycemic control directly or indirectly.

Glucose Lowering Medications		Weight-Loss Medications	Systemic steroids
Insulin or Insulin Secretagogues	Other		
Insulin 
 
Insulin glargine (Lantus; Toujeo; Semglee)
 
Insulin basaglar or biosimilar
 
Insulin detemir (Levemir)
 
Insulin degludec (Tresiba)
 
Insulin NPH (Novolin N; Humulin N)
 
Insulin aspart (Novolog, FlexPen, Fiasp)
 
Insulin Fiasp
 
Insulin lispro (Humalog; Admelog)
 
Insulin glulisine (Apidra)
 
Insulin regular (Novolin R, Humulin R)
 
	Metformin (Glucophage, Glucophage XR, Glumetza, Riomet, Fortamet) Thiazolidinediones 
 
Pioglitazone (Actos)
 
Rosiglitazone (Avandia)
 
 DPP-4 Inhibitors 
 
Sitagliptin (Januvia)
 
Saxagliptin (Onglyza)
 
Linagliptin (Tradjenta)
 
Alogliptin (Nesina)
 
Vildagliptin (Galvus)
 
 Alpha Glucosidase Inhibitors 
 
Acarbose (Precose)
 
Miglitol (Glyset)
 
 Orlistat (Xenical) Lorcaserin (Belviq) Phentermine-Topiramate (Qsymia) Liraglutide (Saxenda) Bupropion-Naltrexone (Contrave) Benzphetamine (Didrex; Regimex) Diethylpropion Phentermine (Adipex; Lomaira; Suprenza) Phendimetrazine (Bontril) Bromocriptine (Parlodel, Cycloset) Colesevelam (Welchol)	Oral formulations 
 
Hydrocortisone
 
Cortisone
 
Prednisone
 
Prednisolone
 
Dexamethasone
 
 Intra-articular injections* 
 
Triamcinolone
 
Methylprednisolone
 
Hydrocortisone
 
	

Glucose Lowering Medications		Weight-Loss Medications	Systemic steroids
Insulin or Insulin Secretagogues	Other		

 
Novolog Mix 70-30 (insulin aspart protamine-insulin aspart)
 
Humalog Mix 75-25 (insulin lispro protamine-insulin lispro)
 
Humalog Mix 50-50 (insulin lispro protamine-insulin lispro)
 
Humulin 70/30 (human insulin NPH-human insulin regular)
 
Novolin 70/30 (human insulin NPH-human insulin regular)
 
Ryzodeg (insulin degludec-insulin aspart)
 
	SGLT-2 Inhibitors 
 
Canagliflozin (Invokana)
 
Dapagliflozin (Farxiga)
 
Empagliflozin (Jardiance)
 
Ertugliflozin (Steglatro)
 
 GLP-1 agonists / dual GLP-1/GIP agonists 
 
Exenatide (Byetta; Bydureon)
 
Liraglutide (Victoza)
 
Dulaglutide (Trulicity)
 
Albiglutide (Tanzeum)
 
Pramlintide (Amylin)
 
Semaglutide (Ozempic, Rybelsus)
 
Tirzepatide (Mounjaro)
 
 Combination Oral Pills 
 
Alogliptin/Metformin (Kazano)
 
Alogliptin/Pioglitazone(Oseni)
 
Empagliflozin/Linagliptin (Glyxambi)
 
Empagliflozin/Metformin (Synjardy)
 
Canagliflozin/Metformin (Invokamet)
 
Dapagliflozin/Metformin XR (Xigduo XR)
 
Glyburide/Metformin (Glucovance)
 
Glipizide/Metformin (Metaglip)
 
Linagliptin/Metformin (Jentadueto)
 
Rosiglitazone/Metformin (Avandamet)
 
Pioglitazone/Metformin (ActoPlus Met)
 
Pioglitazone/Glimepiride (Duetact)
 
Rosiglitazone/Glimepiride (Avandryl)
 
Sitagliptin/Metformin (Janumet)
 
Sitagliptin/Metformin (Janumet XR)
 
Repaglinide/Metformin (PrandiMet)
 
Pioglitazone/Metformin XR (ActoPlus Met XR)
 
Saxagliptin/Metformin XR (Kombiglyze XR)
 
		
Sulfonylureas			

 
Glimepiride (Amaryl)
 
Glipizide (Glucotrol)
 
Glyburide (Micronase, Diabeta)
 
Tolbutamide (Orinase)
 
			
Meglitinides			

 
Nateglinide (Starlix)
 
Repaglinide (Prandin)
 
			

Glucose Lowering Medications	Weight-Loss Medications	Systemic steroids
Insulin or Insulin Secretagogues	Other	
* Since intraarticular joint injections can have prolonged systemic effects, a single joint injection of any of the following medications will result in subject withdrawal.		
Note: Otic, ophthalmic, and inhaled glucocorticoids WILL be permitted		

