### 7.2 PARTICIPANT DISCONTINUATION/WITHDRAWAL FROM THE STUDY

The study team will only withdraw a participant if any clinical adverse event (AE), laboratory abnormality, or other medical condition or situation occurs such that continued participation would not be in the best interest of the participant. Participants who develop diabetes mellitus during the course of the study **will be eligible** to continue, and all new medications that are initiated for glycemic control will be reported. Subjects who sign the informed consent form, and are randomized and receive the study intervention, and subsequently withdraw, or are withdrawn or discontinued from the study, will not be replaced.

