## 9.3 POPULATIONS FOR ANALYSES

Consistent with the **intention-to-treat (ITT)** principle, results of all study participants will be evaluated according to initial randomization regardless of whether they adhered to their assigned treatment and regardless of protocol violations or deviations. Analyses of effectiveness endpoints, however, will exclude participants who withdraw from the study or withdraw consent. Effectiveness analyses will be performed for the ITT population. All primary statistical analyses of effectiveness measures will be unadjusted and two-sided tests of significance will be used. A per-protocol analysis will also be conducted using the population of program completers in each group, as defined in Section 3.3, to benchmark outcomes against CDC standards.

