#### 9.4.5 COVARIATE ADJUSTMENT

We anticipate that randomization will minimize differences in participant characteristics that may be associated with the primary or secondary endpoints between the two groups. All primary statistical analyses will be unadjusted. However, if we identify differences in participant baseline characteristics, or exposure to potential confounders during the course of the study (e.g. steroid use, antihyperglycemic use), sensitivity analyses will be conducted to include these variables as covariates in multivariable logistic or linear regression models, as appropriate. These adjusted analyses will be viewed as supportive in interpreting the findings of the unadjusted analyses.

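### Section 6.5 withdraws a participant after one joint steroid injection, 7.2 limits withdrawal to a best-interest test, and 9.3, read naturally, then drops that randomised person from the effectiveness analyses

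*Combined protocol and SAP*

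**What the plan says.** - **Section 6.5 (Prohibited Medications).** The table lists glucose-lowering drugs, weight-loss drugs and systemic steroids. The stated reason is that "These medications can influence glycemic control directly or indirectly". The lead-in describes use "whether taken alone or as a component of a combination drug within previous 3 months". A footnote attached only to intra-articular steroids adds that "a single joint injection of any of the following medications will result in subject withdrawal".
- **Section 7.2 (Withdrawal).** "The study team will only withdraw a participant if any clinical adverse event (AE), laboratory abnormality, or other medical condition or situation occurs". Each of these grounds carries a further test, namely whether "continued participation would not be in the best interest of the participant". The same section keeps participants who develop diabetes in the study and has their new glucose-lowering drugs reported.
- **Section 8.4.7 (Pregnancy).** Participants who become pregnant are withdrawn.
- **Section 9.3 (Populations).** The intention-to-treat statement covers all participants as randomised, whatever their adherence or protocol deviations. It is followed by: "Analyses of effectiveness endpoints, however, will exclude participants who withdraw from the study or withdraw consent".
- **Sections 9.4.5 and 9.4.7.** On-study steroid exposure may enter adjusted models. In the words of 9.4.5, in the event of "exposure to potential confounders during the course of the study (e.g. steroid use, antihyperglycemic use), sensitivity analyses will be conducted".

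**The concern.** Section 6.5 requires withdrawal because of a drug effect on glycaemic measures. Section 7.2 allows withdrawal only on a test of the participant's interest. A site cannot tell from these two texts what follows an injection given during the study.

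The data consequence matters more. If the participant is withdrawn and 9.3 then excludes withdrawals, membership of the primary analysis set depends on something that happened after randomisation. Treatment allocation is open, so care-seeking and reporting could differ by arm. Section 8.4.3.3 lists musculoskeletal injury related to physical activity as an expected event, so a link between joint problems, lower activity and failure on the endpoint is plausible, though the documents do not show one. Weight loss alone can meet the primary endpoint, so exclusion also discards outcome information that goes beyond the A1C measurement the rule is meant to protect. In a non-inferiority comparison, losing failures from the digital arm moves the result towards the sponsor's hypothesis; losing them from the coach arm moves it the other way.

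**Working it through.** **1. Is the footnote about enrolled people?** The three-month lead-in in 6.5 is eligibility wording, and exclusion criterion 5 in 5.2 cites 6.5 for the same window. Against that, the footnote speaks of withdrawing a subject, while 5.4 calls people who are never randomised screen failures. The on-study reading is the better one, but it is not certain.

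**2. Does 7.2 cover the injection?** Its list ends with a catch-all for other conditions or situations, tied to the participant's interest. The reason given in 6.5 is a drug effect on glycaemic control, which fits that test poorly.

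**3. Does 9.3 reach team-initiated withdrawal?** It names leaving the study separately from withdrawing consent, so it covers more than the participant's own refusal. The natural reading includes withdrawal by the team. However, 7.2 distinguishes those who withdraw from those who are withdrawn, and 9.3 does not repeat that distinction.

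**4. The plan's own sample size.** Inputs from 9.1 and 9.2: 50% success in both arms, margin 0.15, one-sided 5%, 80% power, 25% attrition.

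n per arm = (1.645 + 0.842)² × 2 × 0.5 × 0.5 / 0.15² = 137.4, rounded up to 138, or 276 in total. Then 138 / 0.75 = 184, or 368 in total. Both stated figures reproduce.

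**5. Size of the possible shift.** No injection frequency is given, so the removed fraction f is an assumption. With success rate p in an arm and q among those removed from it:

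rate among those left = (p − f·q) / (1 − f), so shift = f·(p − q) / (1 − f).

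The extreme case has one arm only and q = 0. Sections 9.1 and 9.2 give p = 50% for planning; 9.1 expects 30–40% for the coach arm under intention to treat.

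| f (of 184) | p = 30% | p = 40% | p = 50% |
|---|---|---|---|
| 1% (about 2) | 0.3 | 0.4 | 0.5 |
| 2% (about 4) | 0.6 | 0.8 | 1.0 |
| 5% (about 9) | 1.6 | 2.1 | 2.6 |

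(Percentage points. For the last row: 0.30/0.95 = 31.6%, 0.40/0.95 = 42.1%, 0.50/0.95 = 52.6%.)

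If those removed would have succeeded half as often as their arm (q = p/2), the 5% row halves to 0.8, 1.1 and 1.3. If q = p, the shift is zero. If both arms have the same p and lose the same fraction with the same q, the difference between arms does not change.

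**6. Power.** If these withdrawals fall within the planned 25% attrition, power is unchanged at about 80%. If they came on top, a further 5% would leave about 129 per arm and 77.7% power. The issue is selection rather than sample size.

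**The case against.** The case for leaving this alone has several parts.

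- **A three-way contradiction with 9.4.5 and 9.4.7.** A reader might infer that the plan both expels steroid users and adjusts for them. The documents do not support that. The footnote covers intra-articular injections only, oral steroids sit in the same table without it, and the analysis sections refer to steroids in general. Retained oral users could supply the covariate. These sections are weak support at most.
- **7.2 as a closed list.** A reader might infer that 7.2 forbids this withdrawal. It has a catch-all, and 8.4.7 requires withdrawal for pregnancy although 7.2 does not name it. So 7.2 is not a complete inventory. The mismatch of reasons stands; a flat prohibition does not.
- **Exclusion from analysis as explicit text.** It is the natural reading of 9.3 but still an inference, for the reason in step 3.
- **A demonstrated bias between arms.** Section 8.4.3.3 also says that no intervention-related events are anticipated, both programmes promote activity, and nothing ties injuries to injections. A difference by arm is possible, not shown.
- **A narrow case.** The harm comes from 9.3's rule on withdrawals of every cause, and injections may be rare. That is fair, and it is why the remedy belongs in 9.3.

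What remains is that 6.5 and 7.2 disagree on the ground for withdrawal, and that 9.3 contradicts its own intention-to-treat statement for anyone withdrawn under a protocol rule.

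**Conclusion.** The point holds in a limited form. Sections 6.5 and 7.2 must be reconciled, including the scope of the footnote. Independently of how that is settled, 9.3 as naturally read lets a post-randomisation event take randomised participants out of the effectiveness analyses, and pregnancy withdrawals under 8.4.7 raise the same problem.

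The size is unknown. The 1.6 to 2.6 points are an illustrative bound for an assumed 5% removal. They correspond to 1.6/15 = 11% to 2.6/15 = 18% of the margin, and they rest on one arm only being affected and every removed participant being a failure. Relaxing either assumption makes them smaller. The figures do not show that the trial's conclusion would change. They show that an avoidable source of selection has been written into the analysis rule. A correction is worthwhile because it costs little, not because a large bias has been established.

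**What to change.** 1. **Reconcile 6.5 and 7.2.** State whether the footnote applies on study or only at eligibility, and make the grounds for withdrawal agree across 6.5, 7.2 and 8.4.7. Which clinical rule to keep is for the investigators.
2. **Separate withdrawal from data handling in 9.3.** State that participants withdrawn by the study team, or exposed to a prohibited medication, remain in the intention-to-treat set in their randomised arm. Use the 12-month outcomes already scheduled where consent to follow-up remains.
3. **Name a missing-data method for the rest.** Section 9.4.2 specifies multiple imputation only for physical-activity data. Weight and A1C for participants without a 12-month visit need a stated method too.
4. **Report exposure.** Tabulate prohibited-medication exposure and team-initiated withdrawals by arm, and examine exposure in a sensitivity analysis. Say that adjusting for an exposure arising after randomisation can itself introduce bias and is supportive only.

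The cost is protocol wording and a little more analysis work. No visits are added to the schedule.

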## 6.6 RESCUE MEDICINE

Not applicable. If a participant has an A1C measurement of 6.5% or greater during the course of the trial (consistent with possible type 2 diabetes), a letter will be sent to their primary care physician for consideration of further evaluation Section 11.19). The decision to use antihyperglycemic medications for participants diagnosed with type 2 diabetes will be at the discretion of their treating clinician.

## 7 STUDY INTERVENTION DISCONTINUATION AND PARTICIPANT DISCONTINUATION/WITHDRAWAL

### 7.1 DISCONTINUATION OF STUDY INTERVENTION

Given the focus of this study on increasing PA and promoting healthy diet and weight loss, we do not anticipate any serious adverse events that would require discontinuation of the study intervention. For participants who do not engage with the study intervention, whether randomized to the dDPP or hDPP, all efforts will be undertaken by the research coordinator to keep the participant in the study for assessment of efficacy and adverse events.

### 7.2 PARTICIPANT DISCONTINUATION/WITHDRAWAL FROM THE STUDY

The study team will only withdraw a participant if any clinical adverse event (AE), laboratory abnormality, or other medical condition or situation occurs such that continued participation would not be in the best interest of the participant. Participants who develop diabetes mellitus during the course of the study **will be eligible** to continue, and all new medications that are initiated for glycemic control will be reported. Subjects who sign the informed consent form, and are randomized and receive the study intervention, and subsequently withdraw, or are withdrawn or discontinued from the study, will not be replaced.

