## 3.2 PRIMARY ENDPOINT

The trial is designed as a non-inferiority trial to evaluate whether the Sweetch dDPP is at least as effective as hDPPs on participant attainment of the CDC's benchmark for type 2 diabetes risk reduction, defined as one or more of the following:

- At least 5% weight loss by 12 months
- At least 4% weight loss at 12 months and at least 150 minutes/week of physical activity measured using monthly serial Actigraphy and averaged over months 1-11)
- At least a 0.2% reduction in hemoglobin A1C by 12 months (for participants whose A1C result obtained at baseline study visit is between 5.7% and 6.4%).

Thus, the prospectively defined primary endpoint will be a binary endpoint at 12 months, defined as 1 if at least one of the CDC "success" outcome measures is achieved and 0 if none are achieved. The primary endpoint was selected to align with the current CDC standards for full recognition of DPP programs (effective May, 2021). According to the CDC, participants may demonstrate type 2 diabetes risk reduction by fulfilling one or more of the above outcomes, and, given the broad range of eligibility criteria for the DPP (see Section 5.1), not all DPP participants are eligible to demonstrate success using each of three outcomes in our composite endpoint. Specifically, the A1C change measure can only be used for participants whose baseline measure is in the prediabetic range of 5.7% to 6.4%. These standards require that at least 60% of participants in a given DPP meet the endpoint for attainment of full recognition in order to become a Medicare DPP supplier. The CDC's Standards and Operating Procedures are subject to change during the course of the study. Should the benchmarks for type 2 diabetes risk reduction change prior to completion of the trial, to the extent possible (i.e. assuming we have collected required data during the trial), we will also analyze our outcomes to align with the updated benchmark.

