## 9.2 SAMPLE SIZE DETERMINATION

Under a 1:1 randomization design, with a significance level (alpha) of 5% and 80% power, and assuming 50% of the participants achieve the primary outcome in both arms, 138 participants are required to enroll in each of the two arms, for a total study sample size of  $n = 276$ . Assuming a conservative attrition rate of 25% at 12 months, the adjusted sample size is set to 184 per group (368 total) to ensure the minimal necessary analyzable sample of 276 is retained. If there is truly no difference between the hDPP and dDPP, then 276 participants are required to be 80% sure that the upper limit of a one-sided 95% confidence interval will exclude a difference in favor of the hDPP of more than 15%. While it was previously noted that  $\pi_s$  will be closer to the 30-40% range, we used 50% in the non-inferiority sample size calculations as this choice yields the largest necessary sample size among all choices for  $\pi_s$ , and thus makes the study robust, in terms of statistical power, to other values for  $\pi_s$ .

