#### 9.4.7 ANALYSIS OF THE PRIMARY EFFICACY ENDPOINT(S)

The primary effectiveness endpoint will be analyzed using an intention to treat approach (ITT) using logistic regression models, where attainment of the CDC's benchmark for type 2 diabetes risk reduction will be the dependent variable and treatment group the

primary exposure variable. Covariate-adjusted models will include any variables that are identified to be statistically significantly different on univariate analysis between the two treatment groups at baseline or over the study period, including use of medications that could influence blood glucose (antihyperglycemics, steroids) and incident diabetes.

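### Success reached on drugs started during the study counts as programme success, and the only planned handling is covariate adjustment for post-randomisation variables

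*Combined protocol and SAP*

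**What the plan says.** Section 3.2 makes the primary endpoint binary at 12 months: one or more of three criteria must be met. One of them is "At least a 0.2% reduction in hemoglobin A1C by 12 months", for participants whose baseline value is in the prediabetes range; 5% weight loss alone is another. None carries a condition about drugs started during the study or about incident diabetes.

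Section 7.2 keeps participants who develop diabetes in the study and says that "all new medications that are initiated for glycemic control will be reported". Section 6.6 adds: "The decision to use antihyperglycemic medications for participants diagnosed with type 2 diabetes will be at the discretion of their treating clinician". Section 9.3 analyses participants as randomised whatever their deviations, excluding those who withdraw, and states: "All primary statistical analyses of effectiveness measures will be unadjusted and two-sided tests of significance will be used".

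The planned handling of on-study drugs is covariate adjustment. Section 9.4.5 foresees supportive sensitivity models if the arms are found to differ at baseline or in exposures such as steroids and antihyperglycemics. Section 9.4.7 puts into the adjusted model of the primary endpoint any variable that differs significantly between arms at baseline or during the study, "including use of medications that could influence blood glucose (antihyperglycemics, steroids) and incident diabetes". Weight-loss drugs are on the section 6.5 list but are named in neither 7.2 nor 9.4.7.

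**The concern.** A participant could reach an A1C of 6.5% at month 6, be prescribed a drug, finish 0.2 points below baseline or 5% lighter, and be scored 1 for diabetes risk reduction. The same participant could count as incident diabetes, a secondary endpoint in 3.3. If drugs produce successes in both arms, the arms can look more alike than the programmes made them. In a superiority trial that would usually be conservative. In a non-inferiority trial it can help the claim, particularly if participants who do poorly on the app are prescribed drugs more often.

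The planned adjustment does not answer this. Drug use and incident diabetes after randomisation can be consequences of the assigned programme, so conditioning on them can remove part of the treatment effect or introduce bias. Because it depends on an observed difference between arms, the adjustment may never be triggered when starts are equal, which is a case in which dilution occurs.

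**Working it through.** **Step 1: the plan's own figure.** Section 9.2 works "with a significance level (alpha) of 5% and 80% power", "assuming 50% of the participants achieve the primary outcome in both arms", and requires that "the upper limit of a one-sided 95% confidence interval will exclude a difference in favor of the hDPP of more than 15" percentage points.

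n per arm = (1.645 + 0.842)² × (0.5×0.5 + 0.5×0.5) / 0.15² = 137.4, so 138. Then 138/0.75 = 184. Both figures reproduce, and power at 138 per arm is 80.2%. I therefore use one-sided 5% and 138 per arm. Section 9.3 speaks of two-sided tests; if that meant one-sided 2.5%, n would be 175 per arm, but that is a separate matter.

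**Step 2: inputs and formula.** Drug-free success is set at 40% in hDPP, the top of the 30–40% range that 9.1 expects under intention to treat, and 25% in dDPP, exactly 15 points lower. Let h and d be the shares starting a drug in hDPP and dDPP, and q the success rate among starters. The documents give none of these three; all are assumptions. Starters are first taken as a random slice of each arm.

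- Ps = (1−h)×0.40 + h×q
- Pe = (1−d)×0.25 + d×q
- SE = √[Ps(1−Ps)/138 + Pe(1−Pe)/138]
- Chance of claiming non-inferiority = Φ[(0.15 − (Ps−Pe))/SE − 1.645]

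With no starters this is 5.0%. Example with h = 5%, d = 10%, q = 80%: Ps = 0.95×0.40 + 0.05×0.80 = 0.420; Pe = 0.90×0.25 + 0.10×0.80 = 0.305; deficit 0.115; SE 0.0575; Φ(0.035/0.0575 − 1.645) = 15.0%.

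| Starters hDPP / dDPP | Deficit, q = 80% | Chance, scored as observed | Chance, starters scored 0 |
|---|---|---|---|
| 2% / 2% | 14.70 points | 5.6% | 5.6% |
| 5% / 5% | 14.25 | 6.5% | 6.6% |
| 10% / 10% | 13.50 | 8.3% | 8.6% |
| 5% / 10% | 11.50 | 15.0% | 4.1% |
| 10% / 5% | 16.25 | 3.1% | 12.7% |

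**Step 3: direction.** At q = 80% the deficit is 0.15 + 0.40h − 0.55d. It shrinks when h is below 1.375d and grows when h is above it. With equal starts m it is (1−m) × 15 points whatever q is. The size is also sensitive to q: the 5% / 10% case gives 9.8% at q = 50%.

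**Step 4: what failure scoring does.** The last column shows that scoring starters 0 does not undo the dilution when they are an equal random slice, and can itself favour non-inferiority when hDPP has more starters. The result differs if starters come only from participants who would otherwise have failed:

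- Starters are 5% of hDPP and 10% of dDPP: Ps = 0.40 + 0.05×0.80 = 0.44, Pe = 0.25 + 0.10×0.80 = 0.33, deficit 11.0 points, chance 16.9%.
- 10% of the failures in each arm start: Ps = 0.40 + 0.60×0.10×0.80 = 0.448, Pe = 0.25 + 0.75×0.10×0.80 = 0.310, deficit 13.8 points, chance 7.5%.

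In both cases scoring starters 0 returns 40% vs 25%, and the chance returns to 5.0%.

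**The case against.** The strongest reply is that this is a choice of estimand. Section 4.1 says that the trial studies real-world effect with little interference by the study team. Under a treatment-policy reading, the difference with drugs included is the target and the planned test has its nominal error. That stands. A reader might infer from the table that the type I error of the planned test is inflated; it is not. The figures are chances of rejection against a drug-free estimand that the plan has not adopted.

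A reader might also infer that the arms will converge. Nothing in the documents says which arm will start more drugs, and the 10% / 5% case goes the other way.

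Nor do the documents support a large effect. The Markov model text in 9.4.9 expects few conversions to diabetes. A1C is measured after baseline only at 6 and 12 months, so the clinician letter in 6.6 can affect the 12-month endpoint only through the month-6 test. At 1–2% starters per arm the chance is 5.3–5.6%. This limits the diabetes route; it does not bound drug starts without diabetes.

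It can be said that weight-loss drugs are already dealt with, because 6.5 says that listed drugs are not permitted and a footnote there withdraws participants after a joint injection. But 6.5 ties its wording to the previous 3 months, 7.2 gives narrower grounds for withdrawal, and 9.3 drops withdrawn participants from the effectiveness analyses. If starters were withdrawn, they would leave the analysis and not score 1. The text does not settle this.

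Finally, the adjusted models are expressly supportive and cannot by themselves decide the claim. That limits the harm of the covariate choice but does not make it sound.

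**Conclusion.** The point holds in a conditional form. As written, success reached after an on-study drug start or after incident diabetes counts in full, subject to the unresolved wording of 6.5, and the plan does not state this as a deliberate strategy. Relative to a drug-free comparison, it can favour non-inferiority when starts are similar in the arms or more frequent in dDPP, and can work against it when they are sufficiently more frequent in hDPP.

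Under the assumed inputs the chance of a claim at a 15-point drug-free deficit ranges from 3.1% to 15% across the five scenarios, and stays near 5% if starts are rare and balanced. The arithmetic is firm; the start rates, the success rate on drug and the random-slice assumption are not from the documents.

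The firmer part needs no such assumption. The adjustment in 9.4.5 and 9.4.7 conditions on variables that treatment can change, one of them a secondary endpoint. It is triggered only by observed differences and does not name weight-loss drugs. It would not be a reliable check on a non-inferiority result.

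**What to change.** - Keep the primary analysis and state in 9.3 or 9.4.7 that it follows a treatment-policy strategy for on-study drug starts and incident diabetes.
- In 9.4.5 and 9.4.7, restrict covariate adjustment to baseline variables; remove on-study drug use and incident diabetes.
- Pre-specify a supplementary non-inferiority analysis at the same 15-point margin. Score as failure anyone who, before the 12-month measurement, started a glucose-lowering or weight-loss drug on the 6.5 list or met incident diabetes.
- Accompany it with a tipping-point or hypothetical-strategy analysis, since failure scoring alone is not sufficient (step 4).
- Tabulate drug starts by arm, with weight-loss drugs shown separately.
- Reconcile 6.5 with 7.2 and 9.3 on what happens to participants who start a listed drug during the study, and on whether they remain in the analysis.

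The cost is SAP wording and a few extra analyses. Sample size and the primary test do not change. The 11.4 form already asks for all current medications at baseline, 6 and 12 months. Its limit is that drugs started and stopped between visits may be missed; one added question would largely close that gap.
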